7.3.4 Criteria for discontinuation of study treatment

Patients may withdraw from treatment or the study overall at any time at their own request, or they may be withdrawn at the discretion of the Investigator or Sponsor for safety, behavioral reasons, or the inability of the patient to comply with the protocol-required schedule of study visits or procedures. In addition to the drug-specific discontinuation criteria listed in Dose Modification Section and the Dose Limiting Toxicity Section, the following will result in treatment discontinuation:

- Disease progression
- Unacceptable Toxicity
- Subject withdraws consent from the study treatment and/or study procedures.
- Non-compliance as defined as having missed > 40% of required celecoxib doses.
- Dose hold \geq 14 days unless resuming treatment is judged by the Investigator to be in the best interest of the patient.
- Does not require adjuvant radiation.
- Pregnancy
- Significant protocol violation
- The patient refused further treatment
- Study terminated by investigator sponsor
- Lost to follow-up
- Death

7.3.5 Criteria for withdrawal from the study

Subjects will be taken off study for the following:

- Completed study follow-up period
- Disease progression as assessed by the treating investigator.
- The necessity for prohibited treatment (as defined in section 6.4) of sufficient dose and duration to confound the study results as assessed by the treating investigator.

- If, in the investigator's opinion, the continuation of the trial would be harmful to the subject's well-being.
- Development of intercurrent illness or situation which would, in the judgment of the investigator, significantly affect assessments of clinical status and trial endpoints.
- Participant requests to be withdrawn from the study
- Death
- Screen failure

8 TOXICITIES AND DOSE MODIFICATION

This study will utilize the CTCAE (NCI Common Terminology Criteria for Adverse Events) Version 5.0 for adverse event and serious adverse event reporting.

8.1 Dose Modifications

Every effort should be made to administer each investigational product at the planned dose and schedule. In the event of study treatment toxicity, dosing may be interrupted, delayed and/or reduced, only as described in the dose modifications section. In the event of multiple toxicities, treatment/dose modifications should be based on the worst toxicity observed (CTCAE v5.0) and/or the most conservative recommendation for any given toxicity. Patients are to be instructed to notify Investigators at the first occurrence of any adverse symptom.

All dose modifications must be clearly documented in the patient's medical chart and in the CRF. Appropriate follow-up assessments should be done until adequate recovery occurs as assessed by the Investigator.

8.2 Dose Interruptions

Dose interruptions for study treatment-related AEs are allowed as per the recommendations provided in Section 8.4. Doses of celecoxib/placebo that were not administered due to toxicity will not be replaced. In addition to dose interruption, the need for a dose reduction at the time of treatment resumption should also be considered based on recommendations provided in Section 8.4.

Dose interruptions of more than 14 days will result in permanent discontinuation unless resuming treatment is judged by the Investigator to be in the best interest of the patient.

8.3 Dose Reductions

Following dosing interruption due to toxicity, the celecoxib dose may need to be resumed at a reduced dose as per the recommendations provided in Section 8.4. Dose reduction should proceed by decreasing the administered dose by one dose level per table 2.

Once the study treatment has been reduced for a given patient, all subsequent cycles should be administered at that dose level. Intra-patient dose re-escalation is not allowed.

Table 2: Dose Level Reduction

| Agent | Initial Dose | Level -1 |
|-------------------|--------------------|--------------------|
| Celecoxib/placebo | 200 mg twice daily | 100 mg twice daily |

8.4 Adverse Event Management

General treatment modifications for study therapy are provided in table 3 for adverse events that are deemed definitely, probably or possibly related to study therapy. Study therapy should be discontinued upon the second occurrence of an adverse event requiring a dose hold and reduction.

Table 3: Adverse Event Management Guidelines

| Adverse Event | Grade | First Occurrence |
|--|----------------|--|
| Hematology | | |
| Hemoglobin | Grade ≥ 3 | Hold study therapy until recovery to grade 1 and reinitiate at a dose level reduction. |
| Hepato-Biliary | | |
| AST or ALT increase or bilirubin increase | Grade ≥ 3 | Hold study therapy until recovery to grade 1 and reinitiate at a dose level reduction. |
| Renal | | |
| Serum creatinine | Grade ≥ 2 | Hold study therapy until recovery to grade 1 and reinitiate at a dose level reduction. |
| Hyperkalemia | Grade ≥ 2 | Hold study therapy until recovery to grade 1 and reinitiate at a dose level reduction. |
| Skin Reactions | | |
| Rash | Grade ≥ 2 | Hold study therapy until recovery to grade 1 and reinitiate at a dose level reduction. |
| Stevens-Johnson syndrome or toxic epidermal necrolysis | Any | Discontinue study therapy |

| Gastro-intestinal | | |
|---|----------------|---|
| Nausea or vomiting lasting \geq 7 days despite optimal anti-emetic therapy | Grade \geq 2 | Hold study therapy until recovery to grade 1 and reinitiate at a dose level reduction. |
| Diarrhea | Grade \leq 2 | Continue study therapy at the current dose level and initiate appropriate antidiarrheal treatment, hydration, and attention to diet. Maintain close monitoring. |
| | Grade \geq 3 | Hold study therapy until recovery to grade 1 and reinitiate at a dose level reduction. |
| GI Ulceration, Bleeding or Perforation | Any | Discontinue study therapy |
| Cardiovascular | | |
| Hypertension | Grade \geq 3 | Hold until resolution and start appropriate antihypertensive therapy. Once hypertension has resolved to baseline or grade \leq 1, reinitiate celecoxib at one dose reduction. |
| Cardiovascular thrombotic event (e.g. myocardial infarction with elevated troponin or stroke) | Any | Discontinue study therapy |
| Other | | |
| Clinically significant, non-hematological adverse events attributed to the study drug. | Grade \geq 3 | Hold study therapy until recovery to grade 1 and reinitiate at a dose level reduction. |

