5.2 Exclusion Criteria

Yes/No (Response of “yes” = patient ineligible)

5.2.1 _____ Known distant metastatic disease or the tumor is deemed not surgically resectable.

5.2.2 _____ Established in a pain management clinic or has taken opioids regularly for ≥ 6 months.

5.2.3 _____ Known or suspected to be poor CYP2C9 metabolizers based on previous history/experience with other CYP2C9 substrates (such as warfarin, phenytoin).

5.2.4 _____ Known hypersensitivity to celecoxib, aspirin, other NSAIDs, or sulfonamides.

5.2.5 _____ Uncontrolled hypertension defined as blood pressure (BP) > 150 mmHg systolic or > 90 mmHg diastolic on three consecutive reads, taken in one sitting, despite optimal antihypertensive treatment.

5.2.6 _____ Patients with a known history of the following:

- Cerebrovascular accident (CVA), stroke, or cardiovascular thrombotic events (e.g. acute myocardial infarction).
- Chronic heart failure.
- Gastrointestinal bleeding, ulceration, peptic ulcer disease, or perforation of the stomach or intestines.
- Aspirin-sensitive asthma.
- Chronic kidney disease, stage 4 or 5.

5.2.7 _____ Patients with a prior or concurrent malignancy whose natural history or treatment has the potential to interfere with the safety or efficacy assessment of the investigational regimen

5.2.8 _____ The subject has an uncontrolled, significant intercurrent or recent illness requiring systemic therapy, would preclude safe study participation, or is deemed clinically significant by the investigator.

5.2.9 _____ Known HIV infection with a detectable viral load within 6 months of the anticipated start of treatment.

Note: Patients on effective antiretroviral therapy with an undetectable viral load within 6 months of the anticipated start of treatment are eligible for this trial.

5.2.10 _____ Known chronic hepatitis B virus (HBV) or hepatitis C virus infection with a detectable viral load.

Note: Patients with an undetectable HBV viral load on appropriate suppressive therapy are eligible. Patients with an undetectable HCV viral load on appropriate treatment are eligible.

Short Title: RESILIENCE

Version Date: 18APR2023

5.2.11 _____ Subjects taking prohibited medications as described in Section 7.3.2. A washout period of prohibited medications for a period of at least 5 half-lives or as clinically indicated should occur prior to the start of treatment.

I certify that this patient meets all inclusion and exclusion criteria for enrollment onto this study.

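### Table 3 has no hypersensitivity row, so its instruction for a first severe allergic reaction to study drug is to hold and restart at 100 mg twice daily

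*Combined protocol and SAP*

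**What the plan says.** Section 8.4 applies Table 3 to adverse events judged at least possibly related to study therapy. The last row, headed Other, covers "Clinically significant, non-hematological adverse events attributed to the study drug" at grade 3 or higher. Its action at first occurrence is "Hold study therapy until recovery to grade 1 and reinitiate at a dose level reduction". Table 2 has a single reduced level, 100 mg twice daily. The text above Table 3 adds: "Study therapy should be discontinued upon the second occurrence of an adverse event requiring a dose hold and reduction".

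Three Table 3 rows stop the drug at any grade: SJS/TEN, "GI Ulceration, Bleeding or Perforation", and cardiovascular thrombotic events.

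Hypersensitivity is named only among the exclusion criteria. Section 5.2.4 bars patients with "Known hypersensitivity to celecoxib, aspirin, other NSAIDs, or sulfonamides". Section 5.2.6 separately bars aspirin-sensitive asthma and a history of "Gastrointestinal bleeding, ulceration, peptic ulcer disease, or perforation of the stomach or intestines".

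**The concern.** A severe allergic reaction is an event for which most readers would expect an explicit stop. The protocol already treats a known allergy to celecoxib as a reason not to give the drug (5.2.4). Yet a patient who shows that allergy for the first time on study reaches, through a catch-all row, an instruction to take the drug again.

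The stake is patient safety. Table 3 does not ask for the restart to be supervised, and much of the dosing takes place at home. Treating investigators are blinded (4.2), so they would act on the written guidance without knowing the assignment unless they break the blind. There is also a monitoring consequence. The rule in 12.3 counts related grade 3 or higher toxicities that lead to discontinuation, so a severe reaction managed by hold and restart, with no later stop, would not count toward it.

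**Working it through.** No calculation in the plan bears on this point. The check is to trace the event through the text and see where it ends.

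**1. Is there a specific row?** Table 3 has 13 instruction rows:
- discontinue at any grade: SJS/TEN, GI ulceration/bleeding/perforation, cardiovascular thrombotic event (3);
- hold and restart: hemoglobin, AST/ALT/bilirubin, creatinine, hyperkalemia, rash, nausea/vomiting, diarrhea grade 3 or higher, hypertension, Other (9);
- continue: diarrhea grade 2 or lower (1).

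3 + 9 + 1 = 13. None names hypersensitivity, anaphylaxis or angioedema.

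**2. Where does the event land?** Take a patient on 200 mg twice daily with no earlier hold and reduction, who has an attributed grade 3 or higher reaction that is neither rash nor SJS/TEN. It is non-hematological and clinically significant, so it meets the Other row, which has no upper grade limit. The action is hold to grade 1, then restart at Level -1. The restart dose is 100/200 = 0.50 of the starting dose.

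**3. Does other text require a stop?**

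| Section | What it does | Does it settle this event? |
|---|---|---|
| 7.3.3 | Treatment runs until intolerable toxicity, end of radiation or six months | Only by judgment; term not defined |
| 7.3.4 | Unacceptable toxicity makes discontinuation mandatory | Only once the investigator judges it so; term not defined |
| 7.3.4 and 8.2 | Stop for a hold of 14 days or more (7.3.4) or more than 14 days (8.2), each with an investigator override | Does not reach a reaction that resolves sooner |
| 7.3.5 | Off study if the investigator thinks continuing is harmful | Only by judgment |
| 4.2 | Emergency unblinding | Reveals the assignment; does not require a stop |
| 16.4.2 and 16.4.3 | SAE report within one business day, then medical monitor and monthly DSMC meeting | Oversight if the event is serious; does not require a stop |
| 11.2 | Dose modification guidelines are to be applied to attributed events | Points back to Table 3 |

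**4. Is there a general rule that a condition barred at entry is a stop on study?**

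| Barred at entry | Related Table 3 action |
|---|---|
| GI bleeding, ulceration, perforation (5.2.6) | Discontinue |
| Stroke or cardiovascular thrombotic event (5.2.6) | Discontinue |
| Uncontrolled hypertension (5.2.5) | Hold and restart |
| Low hemoglobin (5.1.4) | Hold and restart |
| Raised bilirubin or AST/ALT (5.1.4) | Hold and restart |
| Poor renal function (5.1.4, 5.2.6) | Hold and restart |
| Abnormal potassium (5.1.4) | Hold and restart (hyperkalemia) |
| Hypersensitivity (5.2.4) | No named row; Other row at grade 3 or higher |

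Two of these areas stop and five are hold and restart, so no such rule exists. The difference for hypersensitivity is that the hold-and-restart rows name their event, which shows a choice was made, whereas hypersensitivity gets there only because nothing else catches it.

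**The case against.** The strongest reply is that the protocol already deals with this. Section 7.3.4 makes unacceptable toxicity a mandatory stop, in addition to the dose modification criteria, so Table 3 does not displace it. Table 3 is headed as guidelines, 8.4 calls its contents general modifications, and 8.3 says only that a reduced dose may be needed on resumption. Serious reactions reach the medical monitor and the DSMC. Patients with known hypersensitivity are screened out. Section 4.3 expects about 53 randomized patients at 1:1, so about 26 or 27 would receive celecoxib.

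Much of this stands, and it rules out two stronger readings that a reader might infer. The first is that the protocol compels rechallenge, or offers nothing else. It does not: discontinuation for unacceptable toxicity is a second written route, and 8.4 does not say that a second occurrence is the only ground for stopping. The second is that Table 3 formally contradicts 5.2.4. It does not: 5.2.4 is an entry criterion, and several other entry-barred conditions are hold-and-restart events on study.

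What the reply does not remove is that every route to a stop after a quickly resolving first reaction runs through an undefined term or an individual judgment, while the one instruction specific enough to look up says restart. The authors did not leave GI, thrombotic or SJS/TEN events to that judgment.

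It is also fair to say that the comparator rows act at any grade, whereas the row proposed here starts at grade 3. That matches the range in which the Other row gives the restart instruction. Milder reactions other than rash have no Table 3 action now and would still have none; whether to include them is a clinical choice.

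**Conclusion.** The point holds as a gap in the dose modification guidance and should be fixed. For a first attributed hypersensitivity reaction of grade 3 or higher, other than rash or SJS/TEN, Table 3's specific instruction is to hold and restart at half dose. Stopping is available, and becomes mandatory once the investigator judges the toxicity unacceptable, but no section names hypersensitivity as such a case. Section 5.2.4 is supporting evidence that the protocol regards celecoxib hypersensitivity as a reason not to give the drug; it is not one side of a contradiction.

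The conclusion rests on reading the Other row by its plain wording and assumes the patient is on the starting dose with no earlier hold and reduction. The documents give no rate for these reactions, so the expected number of affected patients is unknown. The case rests on the severity of a possible re-exposure, not on its frequency.

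**What to change.** Add a row to Table 3: hypersensitivity, anaphylaxis or angioedema attributed to study drug, grade 3 or higher: discontinue study therapy, no rechallenge. Add a sentence stating that this row takes precedence over the Other row, and over the rash row when rash is part of such a reaction.

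The cost is a protocol amendment of one row and one sentence, with no extra visits, tests or patients written into the plan. A few more patients may stop study drug, including some on placebo, because attribution is made under the blind. Under 13.3.2, a patient who stops after completing lead-in and surgery remains evaluable for the primary endpoint if radiation starts. One who stops during the 1 to 7 day lead-in may not be. Discontinuations under the new row would count toward the 12.3 stopping rule, which is appropriate for reactions of this severity.

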8.5 Supportive Care

All supportive measures consistent with optimal patient care may be given throughout the study.

8.6 Contraception

Women of childbearing potential are required to use one method of appropriate contraception during trial participation and 5 days after the last dose of study therapy. Childbearing potential is defined as those who have not been surgically sterilized or have not been free from menses for at least 1 year. Appropriate methods of birth controls for women include oral or implanted contraceptives, intrauterine device (IUD), diaphragm with spermicide, cervical cap, abstinence, use of a condom by the sexual partner or sterile sexual partner and also based on the judgment of the investigator.

Acceptable methods of contraception are:

- Single method (one of the following is acceptable):
 - intrauterine device (IUD)
 - contraceptive rod implanted into the skin
- Combination method (requires the use of two of the following):
 - diaphragm with spermicide (cannot be used in conjunction with cervical cap/spermicide)
 - cervical cap with spermicide (nulliparous women only)
 - contraceptive sponge (nulliparous women only)
 - male condom or female condom (cannot be used together)
 - hormonal contraceptive: oral contraceptive pill (estrogen/progestin pill or progestin-only pill), contraceptive skin patch, vaginal contraceptive ring, or subcutaneous contraceptive injection

9 SCHEDULE OF EVENTS

The Schedule of Events table provides an overview of the protocol visits and procedures. Refer to the Study Procedures section of the protocol for detailed information on each assessment required for compliance with the protocol. The Investigator may schedule visits (unplanned visits) in addition to those listed in the Schedule of Events table in order to conduct evaluations or assessments required to protect the wellbeing of the patient. This Schedule of Events will be followed for the entire study.

Short Title: RESILIENCE

Version Date: 18APR2023

Table 4: Schedule of Events

| Examination | Screening ¹ | Pre-Operation ² | Surgery ³ | Post-Operation ⁴ | 5 Weeks Post-Operation | Mid Radiation ⁵ | End of Treatment ⁶ |
|--|------------------------|----------------------------|----------------------|-----------------------------|------------------------|----------------------------|-------------------------------|
| Informed Consent | X | | | | | | |
| Medical History | X | | | | | | |
| Eligibility Criteria | X | | | | | | |
| Vital Signs | X | | | X | | X | X |
| Physical Exam ⁷ | X | | | X | | X | X |
| Karnofsky Performance Status ⁸ | X | X | | X | | X | X |
| Functional Oral Intake Score | X | X | | X | | X | X |
| Hematology ⁹ | X | | | X | | X | X |
| Chemistry ¹⁰ | X | | | X | | X | X |
| Pregnancy Test ¹¹ | | X | | | | | |
| HIV and Hepatitis Serologies ¹² | X | | | | | | |
| Radiation Oncology Consultation | X ¹³ | | | | | | |
| Surgery | | | X ¹⁴ | | | | |
| Celecoxib/placebo ¹⁵ | | | | X | | | |
| Questionnaires ¹⁶ | | X | | X | | X | X |
| Pre-treatment Questionnaire ¹⁷ | | X | | | | | |
| Analgesic Use Record ¹⁸ | | X | | X | | X | X |
| Adverse Events | | | | X | | | |
| Concomitant Medications | X | X | | X | | X | X |
| Telephone Call or Email ¹⁹ | | | | | X | | |

¹ All screening procedures must be completed \leq 28 days prior to surgery.

² This visit may be combined with Screening if all Pre-Operation visit procedures occur \leq 14 days prior to surgery. All pre-operation activities must be completed prior to starting study therapy.

³ All procedures must be completed prior to surgery.

⁴ Post-operation visit will occur 5 to 30 days after surgery.

⁵ Mid-radiation visit will occur 5-35 days after initiation of radiation therapy.

⁶ End of treatment visit will occur 1 to 30 days after the last treatment of radiation.

⁷ Appendix 8: Treating Investigator Patient Assessment Guidance to be filled out by the treating investigator at the time of physical exam.

⁸ See Appendix 8: Treating Investigator Patient Assessment Guidance

⁹ Hematology to include CBC with platelets and differential.

¹⁰ Chemistry to include a complete metabolic panel (CMP).

¹¹ All women of child-bearing potential must have a negative pregnancy test 7 days prior to surgery.

¹² Only required if there is a known history of HIV, hepatitis B, or hepatitis C to confirm eligibility.

¹³ The radiation oncology consultation should be completed prior to registration if possible. This will include a discussion of the indications for adjuvant radiation treatment, a typical treatment course, and the anticipated/possible side effects so the subjects know what to expect if enrolled on trial.

¹⁴ Prior to surgery, the surgical team (physicians, nursing staff, pharmacy, etc.) will be notified about the patients involvement in the trial to ensure standard of care celecoxib and other prohibited therapies are not inadvertently administered.

¹⁵ Patients will complete 1 to 7 days of study therapy prior to surgery and continue twice daily dosing until the last radiation session.

¹⁶ Appendix 3: MDASI Head and Neck Cancer, Appendix 4: EORTC QLQ-H&N43, Appendix 5: Pain Satisfaction Questionnaire, and Appendix 7: Visual Analog Scale for Pain to be completed within 1 month of the scheduled time-points.

¹⁷ Appendix 6: Pre-treatment Questionnaire to be completed at the pre-operation visit.

¹⁸ Patients will be required to record all opioids taken for pain management on Appendix 4: Pain Management Diary while at home. Diary does not need to be maintained during admission post-surgery but should be started when study therapy is started and continue until completion of study therapy.

¹⁹ 5 weeks (\pm 7 days) post-operation the study team will contact the patient to review their medication diary, adverse events, and analgesic use record. If not returning to the study site at this time point, patients will be asked to fax or scan and email their Patient Dosing Diary and Pain Management Diary use records for the study team for review to ensure timely review of study drug compliance.

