10.2 Treatment Period

Once a subject has completed screening, has been found to be eligible, and has been registered, treatment procedures may begin. At the pre-operation visit baseline, questionnaires will be completed and study medication will be dispensed. Patients will be instructed not to begin study medication until 6 days prior to the date of surgery to ensure 5 full days of twice-daily dosing. All pre-operation visit procedures must take place within 14 days prior to surgery unless otherwise noted.

Upon completion of 1 to 7 days of study therapy dosing, patients will undergo head and neck surgery as deemed appropriate by the treating investigator. 14 days (\pm 7 days) after surgery patients will return to the clinic and begin arrangements for adjuvant radiation therapy.

Five to thirty days post-operation every effort should be made to contact the patient to assess study drug compliance and adverse events. For patients not returning to the study site during this time frame, this contact may occur by phone or email. During this contact the study team will check the patient's Dosing Diary, Pain Management Diary, and adverse events. The patient will be asked to scan and email or fax their Dosing Diary and Pain Management Diary for assessment of adherence to the study regimen. However, if the patient does not have access to equipment to do this or is unwilling, failure to obtain the diaries will not be considered a deviation.

During adjuvant radiation, patients will return to clinic for evaluation (Mid-Radiation visit) 5 to 30 days after initiating radiation therapy. Patients will be instructed to continue study therapy twice-daily dosing until completion of their last radiation treatment.

See the Schedule of Events and the Assessments Section for treatment period procedures.

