Appendix 7: Visual Analog Scale for Pain

Subject Number: _____

[figure not shown]
Date: _____

Place an X on the line to indicate your pain intensity averaged as it applies to the past 7 days while at rest, with a swallow, and with a cough.

[figure not shown]
While at rest:

With a Swallow:

With a Cough

Patient Signature

Date

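### The one-month tolerance in footnote 16 lets post-operation pain and QoL questionnaires be completed during radiation, more often on celecoxib if the hypothesised effect occurs

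*Combined protocol and SAP*

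**What the plan says.** Section 9, Table 4, footnote 16 names four forms (Appendices 3, 4, 5 and 7) and says they are "to be completed within 1 month of the scheduled time-points". It does not say before or after, nor whether the month runs from the visit date or extends the visit window.

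The time-points are themselves windows:
- Post-operation (footnote 4): "Post-operation visit will occur 5 to 30 days after surgery".
- Mid-radiation (footnote 5): "Mid-radiation visit will occur 5-35 days after initiation of radiation therapy". Section 10.2 gives a different range: "Mid-Radiation visit) 5 to 30 days after initiating radiation therapy".
- End of treatment (footnote 6): "End of treatment visit will occur 1 to 30 days after the last treatment of radiation".
- Pre-operation (footnote 2): "All pre-operation activities must be completed prior to starting study therapy". Section 10.2 also places the baseline questionnaires at that visit, within 14 days before surgery.

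Recall periods are short. The VAS in Appendix 7 asks for "pain intensity averaged as it applies to the past 7 days". The EORTC module and the pain satisfaction form also cover one week, and the MDASI-HN covers 24 hours.

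Section 13.4.2 analyses the pain score and the two QoL instruments with a Gaussian mixed model containing arm, provider and a patient effect nested in provider. It has no term for visit, time since surgery or radiation status, and no rule classifies a form by its actual date. Section 13.2 plans on radiation starting at a mean of 72 days in one group and 57.2 in the other, with SD 16.2.

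**The concern.** With a recall of one to seven days, the completion date decides which phase of treatment a form describes. A tolerance of a month is long against that recall, and it is long enough to carry a post-operation form past the start of radiation. A form labelled as surgical recovery could then report radiation symptoms.

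This need not be equal noise in both arms. The trial is built on celecoxib bringing radiation forward by about 15 days. If that happens, a late post-operation form is more likely to fall in radiation on celecoxib than on placebo. Because the planned model pools forms without a visit or time term, the arm contrast would then average over a different mix of phases in each arm. Pain control and quality of life are stated secondary objectives, so it is worth knowing what their estimates describe.

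**Working it through.** **Inputs.** Tolerance of 1 month, taken as 30 days (footnote 16). Visit windows from footnotes 4 to 6. Radiation-start means 57.2 and 72 days, SD 16.2, 20 per arm (section 13.2). The historical mean of 72.8 days, also in section 13.2, serves as a check. Normality of the radiation-start day is an assumption.

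**The plan's own figure.** Difference 72 − 57.2 = 14.8. Standard error 16.2 × √(2/20) = 5.12. Noncentrality 14.8 / 5.12 = 2.89 on 38 degrees of freedom. Two-sided power at 0.05 from the noncentral t distribution is 0.804, which reproduces the stated 80%. The same means and SD are used below.

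**Permitted dates if the month is added to the window.**

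| Form | Visit window | Late-only reading | Before-or-after reading |
|---|---|---|---|
| Post-operation, days from surgery | 5 to 30 | 5 to 60 | −25 to 60 |
| Mid-radiation, days from first fraction (Table 4) | 5 to 35 | 5 to 65 | −25 to 65 |
| Mid-radiation (section 10.2) | 5 to 30 | 5 to 60 | −25 to 60 |
| End of treatment, days from last fraction | 1 to 30 | 1 to 60 | −29 to 60 |

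On the before-or-after reading a mid-radiation form can precede radiation. Whether day 65 lies after the last fraction depends on the course length, which section 13.2 and Table 4 do not give.

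**Share already in radiation on day d:** Φ((d − mean) / 16.2).

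| Day of form | Celecoxib (57.2) | Placebo (72) | Placebo (72.8) |
|---|---|---|---|
| 30: last visit day, tolerance unused | Φ(−1.68) = 4.7% | Φ(−2.59) = 0.5% | 0.4% |
| 44: day-14 clinic return plus 30 | Φ(−0.81) = 20.8% | Φ(−1.73) = 4.2% | 3.8% |
| 60: day-30 visit plus 30 | Φ(0.17) = 56.9% | Φ(−0.74) = 22.9% | 21.5% |

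**Averages over timing.** The documents give no distribution of completion dates, so uniform timing is assumed and the share is found by simulation (2 million draws), with placebo mean 72.

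| Visit day | Form offset | Celecoxib | Placebo |
|---|---|---|---|
| Uniform 5 to 30 | Uniform 0 to +30 | 10.6% | 2.2% |
| Uniform 5 to 30 | Uniform −30 to +30 | 5.5% | 1.1% |
| Uniform 7 to 21 | Uniform 0 to +30 | 6.7% | 1.1% |
| Uniform 7 to 21 | Uniform −30 to +30 | 3.4% | 0.5% |

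The last two rows apply if the clinic return at 14 ± 7 days in section 10.2 is the post-operation visit. Per 20 patients, the first row is 2.1 forms against 0.4 (20 × 0.106 and 20 × 0.022), and the second is 1.1 against 0.2.

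A form counts as in radiation from the first fraction onward. A 7-day recall just after that date still covers some days before radiation, so the shares slightly overstate the overlap for the weekly forms.

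**The case against.** The strongest case against is that the size is modest and conditional. The day-60 figures need a visit on its last permitted day and a form a full 30 days later, and the footnote never says that the month is added to the window's edge. On average, one or two forms in 20 are involved on celecoxib. If celecoxib does not move the start of radiation, this source creates no arm difference. Mid-radiation and end-of-treatment visits are tied to radiation dates, so the mechanism does not shift them by arm in the same way. The endpoints are secondary, in a pilot, and reported as differences with intervals. All of this stands, and it limits the weight of the point.

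A reader might also infer more than the documents support:
- **Post-operation forms completed before surgery.** This needs a before-or-after reading of a visit defined as following surgery. On a late-only reading it disappears, and in either case it does not depend on when radiation starts, so it would not differ by arm.
- **A contaminated baseline.** Footnote 2 and section 10.2 already put the pre-operation forms before the first dose, and section 13.4.2 plans no baseline adjustment.
- **Bias against celecoxib.** That needs symptoms to be worse in radiation than in late surgical recovery, which the documents do not show.
- **Damage to swallowing, feeding-tube and opioid results.** Footnote 16 covers only the four questionnaires. The Functional Oral Intake Scale and feeding-tube use are recorded by the investigator, and opioids come from a diary. Only questionnaire items on swallowing are exposed.

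What the objection does not answer is that the tolerance is a stated rule, it is long relative to the recall periods, and nothing in the analysis accounts for when a form was completed.

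**Conclusion.** The concern holds in a limited form. Footnote 16 permits post-operation questionnaires to be completed during radiation. Under the plan's own effect assumption this would happen more often on celecoxib: about 5-11% against 1-2% on average with visits spread over days 5 to 30, somewhat less if visits fall on days 7 to 21, and 57% against 23% only at the extreme.

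The result rests on four assumptions: the month is added to the visit window, one month is 30 days, radiation start is normally distributed, and timing is uniform for the averages. The arm difference arises only if celecoxib shortens the interval from surgery to radiation. The possible consequence is that questionnaire pain and QoL contrasts mix treatment phases differently by arm, in a direction that the documents do not establish. The primary endpoint is not affected. This is a cheap improvement to secondary endpoints, not a threat to the trial's main conclusion.

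**What to change.** 1. In footnote 16, replace "to be completed within 1 month of the scheduled time-points" with a requirement to complete the forms within the existing visit window, and restate that pre-operation forms precede the first dose, as footnote 2 already requires. For the post-operation form, the overlap with radiation is then at most 4.7% against 0.5%, on the last permitted day.
2. Keep late forms in the data with their actual completion date. Do not void a form because radiation has started. That would make validity depend on a post-randomisation event that the drug is meant to move, and would remove more forms on celecoxib if the drug works.
3. In section 13.4.2, add visit and arm-by-visit terms for these questionnaires. Classifying forms by date is not enough alone, because a model without a visit term gives the same arm estimate whatever label a form carries.
4. Add a sensitivity analysis that uses all forms with actual days from surgery and radiation status at completion. Radiation status arises after randomisation, so this analysis should support the main one, not replace it.
5. Reconcile the mid-radiation window, which is 5-35 days in Table 4 and 5-30 days in section 10.2.

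The cost is a line of wording, a completion date on each form, and extra model terms. The downside is that some late forms will not count for their nominal visit.
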